ALP = alkaline phosphatase; BUN = blood urea nitrogen; GGT = gamma glutamyl transferase; LDH = lactic dehydrogenase; RBC = red blood cells.

Protocol 331-201-00079

Any value outside the normal range will be flagged for the attention of the investigator who must indicate whether or not a flagged value is of clinical significance. If one or more values are questionable, the test(s) may be repeated. If the result of any test (or repeat test, if done) is indicated as clinically significant in the samples taken during the screening period, the subject will NOT be enrolled into the trial without the permission of the medical monitor. In addition, follow-up unscheduled laboratory tests should be performed if clinically significant abnormalities are observed. Unscheduled laboratory tests may be repeated at any time at the discretion of the investigator for appropriate medical care. Refer to [Appendix 1](#) for criteria for identifying laboratory values of potential clinical relevance.

The following laboratory test results at screening are exclusionary:

- Platelets $\leq 75000/\text{mm}^3$
- Hemoglobin $\leq 9 \text{ g/dL}$
- Neutrophils, absolute $\leq 1000/\text{mm}^3$
- WBC count $\leq 2800/\text{mm}^3$
- Aspartate aminotransferase (AST) $> 2 \times$ upper limit of normal (ULN)
- Alanine aminotransferase (ALT) $> 2 \times$ ULN
- Creatinine $\geq 2 \text{ mg/dL}$
- HbA1c $\geq 7.0\%$
- Abnormal free T₄, unless discussed with and approved by the medical monitor. (Note: Free T₄ is measured only if result for TSH is abnormal.)
- CPK $> 3 \times$ ULN, unless discussed with and approved by the medical monitor
- QTcF $\geq 450 \text{ msec}$ for males and ≥ 470 for females

The total volume of blood to be collected during the trial per subject is expected to be approximately 150 mL.

A pregnancy test will be conducted in WOCBP prior to trial intervention; results must be available prior to the administration of the IMP. Pregnancy tests can be performed at any point during the trial if pregnancy is suspected.

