5.1.3 Handling of Missing Data

For missing data resulting from early withdrawal from the trial in Phase C, subjects who withdraw early will be censored in the primary efficacy analysis at the time when they withdraw from the trial. For other efficacy variables, two types of analyses will be performed for analyses by visit in Phases B and C: LOCF and OC. The LOCF and OC data sets are defined in Section 5.1.1. The OC data set will be used for analyses at each trial visit and the LOCF data set will be used for analyses at the last visit.

The definitions of weeks for Phase A, B and C are described in the following Table 5.1.3-1 and Table 5.1.3-2. Trial Days are derived for each phase from the formula: Trial Day = Date of assessment - Date of 1st brexpiprazole dosing + 1 in Phase A or B, or Date of randomization in Phase C. Based on the number of trial days, subjects are mapped to the corresponding week in each phase in the summary tables. Only last observation within the same week in each phase is used for the summary tables. The LOCF/OC datasets for Phase A consist of data values obtained from visits at Phase A baseline, and week 1 through week 8 in Phase A. The LOCF/OC datasets for Phase B consist of data values obtained from week 1 through week 12 in Phase B and Phase A baseline as the baseline. The LOCF/OC datasets for Phase C consist of data values obtained from visits (after randomization) from week 2 through week 26 in Phase C (study Week 21 – Week 46).

Note: NA = Not Applicable.

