5.6.2 Laboratory Test Results

Clinical laboratory tests include the routine clinical laboratory measurements, prolactin concentrations, coagulation parameters (PT, aPTT, and INR), HbA1c, cortisol, ACTH, and TSH as well as laboratory tests identified using prospectively defined criteria.

Summary statistics for the clinical laboratory measurements at baseline and post-baseline visits, and summary statistics of changes from baseline to each visit will be presented by treatment group. Incidence of treatment-emergent potentially clinically significant abnormal lab results will also be summarized by treatment groups. Listings of potentially clinically significant abnormalities will also be provided. Criteria of potentially clinically significant lab test abnormalities are provided in Appendix 1.

According to FDA Guidance, laboratory measurements that signal the potential for drug-induced liver injury (DILI) will be reported. An incidence table and a listing will be provided for subjects who meet one or combinations of following criteria:

- 1) ALT or AST $\geq 3 \times$ upper limit of normal (ULN) or baseline value

- 2) increase in bilirubin $\geq 2 \times$ ULN or baseline value

If laboratory tests assessments are repeated for the same visit, the last repeated values are used for summary tables. This is accomplished by sorting patient data by visit date and visit time (if applicable) within the same visit identification. If the lab data are recorded as ranges (i.e., including < or > limit of quantification), these data are not included in the calculations for changes from baseline but included in the calculations for incidences.

Listings and summary tables of clinical laboratory measurements will be presented for Phase B safety sample and Phase C safety sample respectively. Potentially clinically significant laboratory abnormalities for Phase A safety sample will be provided by listings.

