5.6.3 Vital Signs Data

Vital signs include body temperature, heart rate, systolic blood pressure, and diastolic blood pressure. In addition, body weight, waist circumference and body mass index (BMI) are measured. Descriptive statistics will be provided by treatment group, for change from baseline in vital signs parameters. Incidence of treatment-emergent potentially clinically significant vital sign results will also be summarized by treatment groups. Listings of potentially clinically significant abnormalities will also be provided. Criteria for the potentially clinically significant vital sign abnormalities are provided in Appendix 2.

If vital sign assessments are repeated for the same visit, the last repeat values will be used for production of mean change from baseline. This is accomplished by sorting patient data by visit date and visit time (if applicable) within the same visit identification.

Listings and summary tables of vital sign data will be presented for Phase B safety sample and Phase C safety sample. Potentially clinically significant abnormalities in vital sign will be listed by subjects for Phase A safety sample.

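### SAP 5.6.2 does not limit the last-repeat rule to means and change, so a laboratory abnormality that is normal on same-visit repeat may be left out of the incidence tables

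*SAP*

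**What the plan says.** **Laboratory tests (SAP 5.6.2).** The repeat rule reads "If laboratory tests assessments are repeated for the same visit, the last repeated values are used for summary tables". The value is selected as follows: "This is accomplished by sorting patient data by visit date and visit time (if applicable) within the same visit identification". The same section promises two incidence outputs. For clinically significant values: "Incidence of treatment-emergent potentially clinically significant abnormal lab results will also be summarized by treatment groups". For signals of drug-induced liver injury: "An incidence table and a listing will be provided for subjects who meet one or combinations of following criteria". It also plans listings of abnormalities. Values recorded as ranges are treated differently by type of output: "these data are not included in the calculations for changes from baseline but included in the calculations for incidences".

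**Vital signs (SAP 5.6.3).** The parallel rule is narrower: "the last repeat values will be used for production of mean change from baseline".

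**ECG (SAP 5.6.4).** This section counts a patient once if there is one or more abnormality in the period. It also applies the term summary tables to ECG abnormalities.

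**Week mapping (SAP 5.1.3).** "Only last observation within the same week in each phase is used for the summary tables".

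**Protocol 3.7.3.2.** "If one or more values are questionable, the test(s) may be repeated". The same section asks for unscheduled follow-up tests when a clinically significant abnormality is seen.

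**The concern.** The rule has no stated exception, and it stands in a section whose outputs include incidence tables. A programmer who follows it literally would carry only the last same-visit value into those tables.

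Repeats are not a random sample of results. Under Protocol 3.7.3.2 they are prompted by values that look questionable or abnormal, so replacing the first value with the last mostly removes abnormal results and seldom adds one.

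Safety and tolerability form the trial's secondary objective. If the literal reading were programmed, the abnormality and liver-injury tables would be understated and could disagree with the listings beside them.

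**Working it through.** The documents give no figure for this rule, so there is none to reproduce. The check is a comparison of text, followed by an illustration of size.

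**1. Does the rule reach the incidence tables?**
- SAP 5.6.2 says summary tables and names no exception. It also says that incidence is summarized, and Protocol 7.6.2 uses the same verb for laboratory incidence.
- SAP 5.6.4 uses summary tables for abnormality output, so the term in this SAP is not confined to means.
- SAP 5.6.3 limits its own rule to mean change; 5.6.2 lacks that limit.
- SAP 5.6.2 separates change from incidence for range-type values, so the distinction was in view, but it was not applied to repeats.

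The literal reading therefore includes the incidence tables, although the text does not say so outright.

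**2. Could the abnormality be counted at another visit?** Protocol Tables 3.7-2 and 3.7-3 schedule one hematology and chemistry panel in Phase B (Week 20 or early termination) and one in Phase C (Week 46, early termination or relapse). Usually no other scheduled panel in the phase could restore the subject to the count.

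**3. Illustration of size.**
- p = incidence when any value counts (assumed).
- f = share of abnormal results repeated under the same visit identification and normal on the last repeat (assumed).
- n = 225 subjects per arm (SAP section 4).
- Reported incidence = p × (1 − f); reported subjects = 225 × p × (1 − f).

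| p | any value counts | f = 0.1 | f = 0.3 | f = 0.5 |
|---|---|---|---|---|
| 2% | 4.5 subjects | 4.05 (1.8%) | 3.15 (1.4%) | 2.25 (1.0%) |
| 5% | 11.25 | 10.125 (4.5%) | 7.875 (3.5%) | 5.625 (2.5%) |
| 10% | 22.5 | 20.25 (9.0%) | 15.75 (7.0%) | 11.25 (5.0%) |

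**4. Effect on the comparison of arms.** With the same f in both arms, the difference becomes (p1 − p0) × (1 − f), while the ratio p1/p0 is unchanged. Example: p1 = 5% and p0 = 2% give a difference of 3 points and a ratio of 2.5. At f = 0.5 the difference is 2.5 − 1.0 = 1.5 points and the ratio is still 2.5.

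A second model lets f depend on how far values lie above the limit. First and repeat values are bivariate normal with correlation 0.5 to 0.85. Placebo incidence is 2%, the drug shifts values by 0.3 SD, and 30% to 80% of abnormal values are repeated (all assumed). The difference falls from 1.97 points to between 0.83 and 1.73. The risk ratio moves from 1.99 to between 2.02 and 2.24. The absolute difference shrinks; the ratio does not move toward 1.

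**The case against.** **The wording is unclear rather than an express exclusion.** SAP 5.6.2 names by-visit statistics, incidence, and the liver-injury table and listing as separate outputs, and never calls the liver-injury table a summary table. A by-visit reading is open. This stands, and it is why the point says that subjects may be excluded. A reader might infer that the SAP removes such results from every table; it does not say that.

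**SAP 5.6.4 already counts anyone with at least one abnormality.** Its paragraph opens in general terms, which is real evidence that an any-value count was intended. But it stands under the ECG heading, 5.6.2 does not refer to it, and if it governed laboratory data it would conflict with the last-repeat rule. It does not settle the matter.

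**The reach is limited.** The rule covers only repeats under the same visit identification. If unscheduled follow-up tests carry their own identification, it does not replace the original; the documents do not say how they are labelled. The last-in-week rule in SAP 5.1.3 might displace the original, but its setting is missing data and week mapping, so applying it to laboratory incidence is an inference. This stands.

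**Important cases have other routes.** Listings are planned. Protocol 5.1 makes a medically relevant laboratory value an adverse event. Protocol 5.4 requires immediate reporting of raised transaminases with raised bilirubin. These limit the harm but do not replace a correct incidence table.

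**Stronger claims about size or signal.** A reader might infer that the rule loses a large, known share of cases. Under the assumptions of 1% to 5% incidence, correlation 0.5 to 0.85 and 30% to 80% repeated, the loss is 13% to 70%, but that range only restates its inputs. A reader might also infer that the rule makes the arms look alike. This holds for the absolute difference but not for the risk ratio. Persistent elevations tend to survive a repeat, and a repeat that is newly abnormal is kept.

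**Conclusion.** The point holds as a drafting defect with a safety consequence. Read literally, SAP 5.6.2 lets the last same-visit repeat decide whether a subject enters the clinically-significant and liver-injury incidence tables. The direction is understatement in both arms, with a smaller absolute difference. This rests on repeats being prompted mainly by questionable or abnormal values and on each of Phases B and C having one scheduled panel.

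The size cannot be derived from the documents: neither the share of values repeated under the same visit identification nor the share that normalise is given. The figures above are illustrations. The primary efficacy analysis is not affected. The correction should be made before the tables are programmed.

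**What to change.** In SAP 5.6.2:
- Restrict the last-repeat rule to by-visit summary statistics and change from baseline, in line with 5.6.3.
- For the clinically-significant and liver-injury incidence tables, count a subject with any on-treatment value that meets the criterion, whether original, repeat or unscheduled. State that the counting rule in 5.6.4 applies to laboratory data.
- State that the last-in-week rule in 5.1.3 does not apply to these tables.

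The cost is a sentence or two in the SAP, with no new data and no change in conduct. Reported incidences may rise slightly and will include some transient values that a repeat did not confirm; the listings, which give the individual values, let a reader identify these.

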5.6.3 Vital Signs Data

Vital signs include body temperature, heart rate, systolic blood pressure, and diastolic blood pressure. In addition, body weight, waist circumference and body mass index (BMI) are measured. Descriptive statistics will be provided by treatment group, for change from baseline in vital signs parameters. Incidence of treatment-emergent potentially clinically significant vital sign results will also be summarized by treatment groups. Listings of potentially clinically significant abnormalities will also be provided. Criteria for the potentially clinically significant vital sign abnormalities are provided in Appendix 2.

If vital sign assessments are repeated for the same visit, the last repeat values will be used for production of mean change from baseline. This is accomplished by sorting patient data by visit date and visit time (if applicable) within the same visit identification.

Listings and summary tables of vital sign data will be presented for Phase B safety sample and Phase C safety sample. Potentially clinically significant abnormalities in vital sign will be listed by subjects for Phase A safety sample.

5.6.4 ECG Data

For the analysis of QT and QTc, data from three consecutive complexes (representing three consecutive heart beats) will be measured to determine average values. The following QT corrections will be used for reporting purposes in the clinical trial report:

- 1) QTcB is the length of the QT interval corrected for heart rate by the Bazett formula: $QTcB=QT/(RR)^{0.5}$
- 2) QTcF is the length of the QT interval corrected for heart rate by the Fridericia formula: $QTcF=QT/(RR)^{0.33}$

- 3) QTcN is the length of the QT interval corrected for heart rate by the FDA
Neuropharm Division formula: $QTcN = QT / (RR)^{0.37}$

The potentially clinically significant ECG abnormalities will be listed by subject. The incidences of abnormal ECGs of potential clinical significance will be tabulated.

Descriptive statistics of change from baseline in heart rate and ECG intervals will be provided. Criteria for potentially clinically significant ECG abnormalities are provided in Appendix 3. The listings and summary tables of ECG abnormalities will be provided for Phase B safety sample and Phase C safety sample, and only the listings will be provided for Phase A safety sample.

In summarizing the incidence of abnormalities, a patient must have had an evaluation that met abnormality criteria by the end of trial, i.e., last contact date. Incidence rate is calculated as the number of patients having at least one abnormality within a trial period divided by the number of patients who are both exposed to the trial medication and have an on-treatment evaluation within that trial period.

5.6.5 Physical Examination

Physical examination findings will be listed by subject for each trial phase.

5.6.6 Extent of Exposure

5.6.6.1 Extent of Exposure to Brexpiprazole and Placebo

The start date of double-blind study therapy - brexpiprazole or placebo - will be the first day of double-blind dosing. The number and percentage of patients who receive brexpiprazole/placebo will be presented by phase, week, and treatment group for the Safety Sample of Phase C. This summary will be performed for Enrolled Sample for Phases A and B.

The mean daily dosage will be summarized by visit and treatment group using descriptive statistics. The mean daily dosage per patient per week will be determined for each week of the study. This will be calculated by dividing the sum of individual total doses by the number of days in the week interval. The summary will contain for each treatment group the number of patients receiving double-blind study medication, and the mean and range of the mean daily dose for each week.

5.6.6.2 Extent of Exposure to ADT

The number and percent of patients who receive an ADT in Phase C will be presented by visit, by ADT treatment group, and by double-blind treatment group for the Safety Sample. A similar summary will be prepared for Phase B. For each ADT, the mean daily dose will be calculated in the same way as for double-blind study medication.

Summaries will be presented for ADT administered to patients in the ADT Sample during Phase A and Phase A+ Sample during Phase A+.

In addition, the mean daily dosage of ADT will be summarized for the ADT Sample during Phase A and the Phase A+ Sample during Phase A+ by week and by ADT group using descriptive statistics.

5.6.7 Other Safety Data Analysis

5.6.7.1 Suicidality Data

Suicidality monitored during the trial using the C-SSRS will be summarized as the number and percentage of subjects reporting any suicidal behavior, ideation, behavior by type (4 types), ideation by type (5 types), and treatment-emergent suicidal behavior and ideation.

Summary tables of C-SSRS will be provided for Phase B safety sample and Phase C safety sample. Suicidality is defined as report of at least one occurrence of any type of suicidal ideation or at least one occurrence of any type of suicidal behavior during assessment period (count each person only once).

Treatment emergent suicidal behavior and ideation is summarized by four types: Emergence of suicidal ideation, Emergence of serious suicidal ideation, Worsening of suicidal ideation, Emergence of suicidal behavior.

Emergence of suicidal behavior/ideation is defined as report of any type of suicidal behavior/ideation during treatment when there was no baseline suicidal behavior/ideation.

Emergence of serious suicidal ideation is defined as observation of suicidal ideation severity rating of 4 or 5 during treatment when there was no baseline suicidal ideation.

Worsening of suicidal ideation is defined as a suicidal ideation severity rating that is more severe than it was at baseline.

5.6.7.2 EPS Rating scales

5.6.7.2.1 Analysis of EPS Rating Scales

Descriptive statistics will be provided for change from baseline to end of phase in SAS, AIMS, and BARS scores for Phases B and C safety samples. Results will be summarized by visit. In addition, change from end of Phase B to end of Phase C in scores for the SAS, AIMS (total of the first 7 item scores), and BARS scales will be evaluated using ANCOVA with baseline value as covariate and treatment and center as factors. OC data sets will be used in the analyses of these EPS scales. In addition, analyses will be

performed using the maximum (i.e. the worst) value observed during Phase C and the last visit data to determine the change from baseline score. The ANCOVA model for change at the last visit and for change to the maximum value will include the Phase C baseline, study center and treatment group. The same analyses will be performed on the AIMS individual item scores 8, 9, and 10. In addition, incidence of BARS Global Clinical Assessment of Akathisia during Phase B and C by severity category will be provided. Analyses of these EPS rating scales will be performed for the Safety Sample.

5.6.7.2.2 Technical Computational Details for EPS Rating Scales

- 1) The SAS total score is the sum of the rating scores for 10 items from the SAS panel in the CRF. The SAS Total Score is un-evaluable if less than 8 of the 10 items are recorded. If 8 or 9 of the 10 items are recorded, the Total SAS score is the mean of the recorded items multiplied by 10 and then rounded to the first decimal place.
- 2) The AIMS movement rating score is the sum of the rating scores for facial and oral moments (i.e., item 1 - 4), extremity movements (i.e., item 5 - 6), and trunk movements (i.e., item 7). The AIMS Total score is un-evaluable if less than 6 of the 7 items are recorded. If 6 of the 7 items are recorded, the Total Score is the mean of the recorded items multiplied by 7 and then rounded to the first decimal place.
- 3) The BARS score is based only on the item of Global Clinical Assessment of Akathisia.

5.7 Other Outcome Analysis

5.8 Pooling of small centers

In models such as ANCOVA or MMRM with center included as fixed effect, small centers will be pooled. Small centers will be defined as centers that do not have at least one evaluable subject (evaluable with regard to the primary efficacy variable) in each treatment arm in Phase C. All small centers will be pooled to form “pseudo centers” for the purpose of analysis according to the following algorithm. Small centers will be ordered from the largest to the smallest based on the number of evaluable subjects (i.e.,

subjects who have a baseline value and at least one post-randomization value. The process will start by pooling the largest of the small centers with the smallest of the small centers until a non-small center is formed. This process will be repeated using the centers left out of the previous pass. In case of ties in center size, the center with the smallest center code will be selected. If any centers are left out at the end of this process, they will be pooled with the smallest pseudo centers, or if no pseudo centers exist, they will be pooled with the smallest non-small center.

6 References

E. Glimm, W. Maurer and F. Bretz Hierarchical testing of multiple endpoints in group-sequential trials. *Statist. Med.* **2010**, 29 219—228.
